
**B.3. Innovation:** There are six major RCTs on polypills currently on-going or planned, three of these RCTs-TIPS-3, HOPE-3, and HOPE-4, are primary prevention studies, two of them-PROPS and SECURE are secondary prevention trials and PolyIran study is aimed at both primary and secondary CVD prevention. The innovative aspects of the SMAART trial include: **First**, this will be to our knowledge the first study to evaluate the feasibility of a polypill on secondary risk reduction among stroke survivors in resource-limited SSA setting with the potential to generate results that will inform research agenda and policy on the utility of the polypill in other LMICs. **Second**, although SMAART is a phase 2 study, a medium to long-term follow-up of 48-weeks is planned to allow investigators to assess changes in the carotid intima-media thickness, a US Food and Drug Administration approved and validate surrogate marker of CVD risk as a primary outcome measure, and compositely assess the sustainability of adherence to the polypill in LMICs as well as collect preliminary data on blood pressure and lipid control and cardiovascular events. Finally, even if SMAART were not to meet its primary endpoint, we will collect substantive data on feasibility, tolerability, adherence, risk factor control estimates, quality of life, and functionality, which could inform the design and conduct of future studies of the polypill strategy for high vascular risk individuals in SSA.

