### C. PRELIMINARY DATA AND PREVIOUS WORK

**C.1. Questionnaire for Verifying Stroke Free Status in Ghana:** To assure accurate exclusion of stroke mimics, we developed a pictographic version of the Questionnaire for Verifying Stroke Free Status with superior diagnostic properties including 98% certainty for determining stroke-free status, which was validated in 3 languages commonly spoken in West Africa (including Ghana).

**C.2. Stroke types, severity, and outcomes in Ghana:** In a study of stroke patients in Ghana and Nigeria, we recruited 3,000 case-control pairs. 64.4% of strokes were ischemic, 35.6% were hemorrhagic. Of the ischemic strokes, 45.5% were small vessel, 35.5% were large-artery atherosclerosis, and 14.0% were cardio-embolic. Topmost risk factors for stroke in descending order of Population Attributable Risk (PAR) were hypertension (Adjusted OR, 95%CI: 10.72,7.30-15.76), diabetes mellitus 2.24 (1.71-2.94), dyslipidemia 1.89 (1.48-2.41), and cardiac diseases 1.75 (1.22-2.50).

**C.3. Inadequate Risk factor control at one year after stroke in Ghana:** We analyzed data on stroke survivors seen at the Neurology Clinic of Kwame Nkrumah University of Science and Technology (KNUST) in Kumasi, Ghana (site of this proposed study). We found that at baseline 89.8% had hypertension, 23.5% had dyslipidemia and 20.2% had diabetes mellitus. At one year after the index stroke: i) systolic blood pressure (SBP) levels were not within guideline recommended targets in one-third of patients, ii) ~ 2-3 antihypertensive medications were required by most patients, iii) 30% were not on statin treatment, iv) 35% were not on antithrombotic therapy.

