
#### D. APPROACH

**D.1. Overview:** The overarching objective of the Stroke Minimization through Additive Anti-atherosclerotic Agents in Routine Treatment (SMAART) trial is to assess whether a polypill containing fixed doses of 3 antihypertensives, a statin and antiplatelet therapy taken once daily orally would result in carotid intimal thickness regression, improved adherence, and tolerability compared with 'usual care' group on separate individual secondary preventive medications among Ghanaian first time stroke survivors. Our ultimate objective is to design of a future multi center, double-blinded, placebo-controlled, parallel-group, RCT comparing the clinical efficacy of the polypill strategy vs 'usual care' in the African context to derive locally relevant, high-quality evidence for routine deployment of polypill for CVD risk moderation among stroke survivors in LMICs.

**D.2. Design:** SMAART incorporates (i) a pilot randomized controlled trial and (ii) a human capital/institutional capacity building component. We propose a randomized, open label, blinded endpoint clinical trial with the intervention arm assigned to a polypill containing 3 antihypertensives, a moderate/high-intensity statin and Aspirin to be taken orally, once daily in the form of two hard capsules compared with the 'usual care' arm who will continue to take separate, individual secondary preventive medications as prescribed by their physicians. We will assess CIMT changes as a robust intermediary outcome measure for CVD events, adherence, tolerability, and risk factor control rates. Furthermore, a cadre of emerging investigators from Ghana will benefit from the rich

learning environment to be created through the implementation of the RCT and the interactions (2 years) with experts from the Medical University of South Carolina.

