#### **D.4. SMAART (Specific Aims 1 and 2):**

- To evaluate whether a polypill-based treatment strategy vs. usual care will result in carotid intimal media thickness stabilization/regression among recent stroke patients at one year after an index ischemic stroke. (Aim 1)
- To evaluate whether a polypill-based treatment strategy vs. usual care will improve vascular risk reduction drug adherence and tolerability among recent stroke patients at one year after an index ischemic stroke. (Aim 2)

**D.4.1. Study Design:** SMAART is a phase II randomized, open label, blinded endpoint clinical trial to evaluate the effect of a polypill taken once daily orally in improving CMIT regression and adherence to secondary risk reduction drug intake vs. 'usual care' group with separate individual secondary preventive medications among Ghanaians with recent onset stroke/TIA in a single center study.

**D.4.2. Participants:** The participants will include 120 adult Ghanaian recent stroke/TIA patients (within two months of stroke onset) meeting inclusion/exclusion criteria who will be randomly assigned to either intervention or usual care arms.

**D.4.3. Inclusion Criteria:** 1. Above the age of 18 years; male or female; 2. Stroke/TIA diagnosis no greater than two months before enrollment. Ischemic strokes including lacunar, large-vessel atherosclerotic, cardio-embolic subtypes are eligible 3. Subjects with stroke may present with at least one of the following additional conditions: Documented diabetes mellitus or previous treatment with oral hypoglycemic or insulin; documented hypertension >140/90mmHg or previous treatment with anti-hypertensive medications; Mild to moderate renal dysfunction (eGFR 60-30ml/min/1.73m^2); Prior myocardial infarction 4. Legally competent to sign informed consent.

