CVD Risk Factor Control Tertiary/feasibility	1. Blood pressure control will be defined as Systolic BP <140 mmHg and/or diastolic DP <90mmHg or (>135/85mmHg in diabetes patients). Mean change in SBP at month 12 from baseline will be compared in the two treatment groups. 2. Dyslipidemia: control will be defined by change in mean LDL-cholesterol <100mg/dl or <70mg/dl. Mean change in LDL-C at month 12 from baseline will be compared in the two treatment groups.
Incidence of Adverse events Tertiary/feasibility	1. Recurrent stroke: fatal/ severely disabling stroke or non-fatal stroke; Coronary Artery Disease: Acute STEMI/NSTE deaths 2. Re-hospitalization for any CV cause; All-cause mortality

**D.4.9. Sample size justification:** The end of study CIMT value will be subtracted from the baseline CIMT value and divided by the length of follow-up. The rate of change in CIMT (mm/yr) between treatment arms will be tested with a two sided t-test. The rate of change in common CIMT in treated patients is around 0.085 mm/yr with a standard deviation of 0.035. We assume that polypill improvement leads to a halting of CIMT progression with an assumed rate of change of 0.0825 mm/yr. With a two sided alpha of 0.05 and a 90% power we need 82 patients (104 patients with 20% drop-out rate).

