#### F. TIMELINE OF ACTIVITIES:

Activities	YEAR 1				YEAR 2			
	Q1	Q2	Q3	Q4	Q1	Q2	Q3	Q4
Ethics approval and renewal at KNUST and MUSC	X				X			
Hire, orient and train project staff	X							
Data collection instruments & questionnaires	X							
Study subject recruitment and follow-up		X	X	X	X	X	X	X
Training and human capacity building	X	X	X	X	X	X	X	X
Prepare manuscripts, final reports, & grant		X		X		X		X

**F.1. Dissemination:** Yearly reports on progress will be shared with the NIH. Findings from the research study will be disseminated by submitting abstracts and poster presentations at conferences such as the International Stroke Conference and through multiple manuscripts to be published in Open-access journals and results will be disseminated to research participants.

**F.2. Expected Outcomes, Benefits, and Impacts- Translation & Scaling Up:** SMAART will be the first study in Africa to provide pilot data on the safety, feasibility, tolerability, risk factor control rates and intermediate CVD outcome (CIMT) of a polypill strategy for secondary prevention after stroke. The highest risk for recurrent stroke and CVD events occurs within the first year after stroke and the SMAART intervention is targeting this phase to provide prelim data for a future multi-site, multinational study to be conducted across resource-limited centers to evaluate hard CVD events and cost-effectiveness of the polypill, specifically for stroke survivors.

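### Table 1's tertiary risk factor row reverses the blood pressure control rule for diabetic patients and defines LDL control by a change in a mean

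*Combined protocol and SAP*

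**What the plan says.** The CVD Risk Factor Control row of Table 1 (D.4.8), labelled tertiary/feasibility, gives the only definitions of control in the protocol.

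- Blood pressure: "Blood pressure control will be defined as Systolic BP <140 mmHg and/or diastolic DP <90mmHg or (>135/85mmHg in diabetes patients".
- LDL: "control will be defined by change in mean LDL-cholesterol <100mg/dl or <70mg/dl".

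For each factor the row then names a between-arm comparison that does not use these limits. For pressure it reads: "Mean change in SBP at month 12 from baseline will be compared in the two treatment groups". LDL-C has a parallel sentence. The analysis plan (D.4.10) does not define control.

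Control rates are nevertheless a stated product of the trial. B.3 offers them even if the primary endpoint is missed: "we will collect substantive data on feasibility, tolerability, adherence, risk factor control estimates, quality of life, and functionality". D.2 lists them among the assessments: "We will assess CIMT changes as a robust intermediary outcome measure for CVD events, adherence, tolerability, and risk factor control rates". F.2 lists them among the expected outputs: "pilot data on the safety, feasibility, tolerability, risk factor control rates and intermediate CVD outcome (CIMT) of a polypill strategy".

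Diabetic patients will be enrolled. D.4.3 names among the accompanying conditions "Documented diabetes mellitus or previous treatment with oral hypoglycemic or insulin", and C.3 reports for the site's own stroke survivors that "at baseline 89.8% had hypertension, 23.5% had dyslipidemia and 20.2% had diabetes mellitus".

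**The concern.** A control definition has to say, for each patient, yes or no. This row fails in two places.

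1. The pressure rule counts values below the limits as control in general, but values above the limits as control in diabetes. Elsewhere (D.4.3) the greater-than sign with a pressure limit marks hypertension, the opposite of control.
2. The LDL rule compares a change in a mean with what look like limits for an attained level. A group mean has one value per arm and classifies nobody.

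Two further points are left open rather than wrong. The pressure rule does not say whether one or both components must be met. The LDL rule does not say whether its two limits apply to different patients or are two rates to report.

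At stake is a usable, prespecified control rate to carry into the later multi-site study. In an open-label trial it is better not to choose among readings after the data are seen.

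**Working it through.** The plan states no expected control rate, so there is no figure to reproduce. The check is of the logic first, then an illustration of size.

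**Diabetes clause, no assumptions needed**

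- *It replaces the main rule.* 160/100 exceeds 135/85, so it is controlled. 120/75 does not, so it is not controlled.
- *It adds to the main rule by 'or'.* There are four readings, since each rule may need both components or either one.
  - Main rule 'either': a patient who fails it has SBP at least 140 and DBP at least 90. That exceeds 135 and 85, so the clause is met under both of its readings.
  - Main rule 'both', clause 'either': a patient who fails the main rule has SBP at least 140 or DBP at least 90, so the clause is met.
  - Main rule 'both', clause 'both': 150/80 fails each, so some patients remain uncontrolled.

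In three of the four additive readings, then, every diabetic patient is controlled whatever the pressure.

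**Component rule.** 150/80 is controlled if either component suffices and not controlled if both are required.

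**LDL.** If the limits are applied to individual changes, a rise of 60 mg/dl meets both, because 60 < 70 and 60 < 100. With the opposite sign convention the value is -60, which also meets both. No change at all meets both too. Read literally, below 100 or below 70 reduces to below 100.

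**Number of diabetic patients.** 0.202 × 120 = 24.2, about 24 if the C.3 share carries over.

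**Illustration of size.** Assumed, not from the protocol: bivariate normal pressures, SD 20/12, correlation 0.6, and means of 131.4/80, 140/85 and 145/88. The value 131.4 = 140 - 20 × z(2/3) uses C.3's one-third of patients off SBP target and further assumes that this unspecified target is SBP <140. The same-direction comparator mirrors the clause's own 135/85 for arithmetic only, not as a proposed target.

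| | 131.4/80 | 140/85 | 145/88 |
|---|---|---|---|
| Main rule, both | 0.602 | 0.423 | 0.323 |
| Main rule, either | 0.862 | 0.738 | 0.645 |
| Reversed clause alone, both | 0.239 | 0.398 | 0.504 |
| Reversed clause alone, either | 0.528 | 0.701 | 0.787 |
| Main or reversed clause, both in each | 0.824 | 0.802 | 0.808 |

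*Sign alone, clause replaces.* Shift = 0.202 × (reversed - same direction), with the component rule held fixed. The same-direction rate for 'both' is 1 minus the reversed rate for 'either'.

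- 131.4/80: 0.202 × (0.239 - 0.472) = -4.7 points
- 140/85: 0.202 × (0.398 - 0.299) = +2.0 points
- 145/88: 0.202 × (0.504 - 0.213) = +5.9 points

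The 'either' reading gives the same shifts.

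*Sign alone, clause adds.* A same-direction clause lies inside the main rule, so the comparator is the main rule itself.

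- Both: 0.202 × (0.824 - 0.602) = +4.5; 0.202 × (0.802 - 0.423) = +7.7; 0.202 × (0.808 - 0.323) = +9.8 points
- Either: 0.202 × (1 - 0.862) = +2.8; 0.202 × (1 - 0.738) = +5.3; 0.202 × (1 - 0.645) = +7.2 points

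*Component rule alone, main rule.* 0.862 - 0.602 = 26 points; 0.738 - 0.423 = 32 points (31.5); 0.645 - 0.323 = 32 points.

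For scale, the standard error of a rate near 45% with 120 patients is √(0.45 × 0.55/120) = 4.5 points.

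**The case against.** The best defence is that this is a drafting slip in a minor row. The intended direction of the diabetes clause is evident from the rest of its sentence, so an analyst would probably notice and not code 160/100 as controlled. The LDL wording may simply run a level-based definition into the mean-change comparison that follows it, and the two limits may be meant as two rates. The row is tertiary, its named comparisons are mean changes, D.4.10 names no model for a control rate, and the measured values allow any definition to be applied later.

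Most of that stands, and it limits the weight of the point. It does not remove it. The row is the only definition given, and the two below-limit signs in the same sentence came through correctly, so a PDF-reading fault is unlikely, though not excluded. One mistyped sign would not explain the LDL wording or the open component rule. Mean changes do not supply the control rates that B.3, D.2 and F.2 promise.

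Two stronger readings are tempting. A reader might infer that the reversed clause would turn a polypill benefit into apparent harm. The documents do not support this: the stated comparisons bypass the clause, and only about 12 diabetic patients per arm are expected (0.202 × 60). A reader might also credit the sign with shifts as large as -10.6 or +15.9 points. Those figures arise only by comparing readings that also differ in the component rule and, for +15.9, in whether the clause replaces or adds. They do not isolate the sign.

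**Conclusion.** The point holds as a correction to one table row. As written, the diabetes clause gives wrong classifications and the LDL rule gives none; the component rule and the use of the two LDL limits are unsettled. These conclusions rest on the text alone.

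The sizes are illustrative and depend on the assumed means, SDs, correlation, diabetic share and SBP target. Within them, the reversed sign is worth roughly -5 to +10 points on the whole-sample rate, and the unsettled component rule matters more. They show how far the readings differ and do not forecast what the trial would report. The change should be made, but nothing in the primary CIMT analysis, the sample size in D.4.9 or the mean-change comparisons depends on it.

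**What to change.** Before analysis, reconcile the row in Table 1 so that:

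- the diabetes clause runs in the same direction as the main rule and is stated either to replace it or to add to it;
- one component rule, both or either, is stated and applies to both clauses;
- LDL control is judged on each patient's attained value at a stated visit, with a statement of how the two listed limits are used.

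The choice of targets stays with the sponsor. Keep the mean-change comparisons of SBP and LDL-C. The cost is wording only, with no new data. Reported control rates may move in either direction as a result.

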**D.4.4. Exclusion criteria:** 1. Unable to sign informed consent, 2. Contraindications to any of the components of the polypill, 3. Hemorrhagic stroke, 4. Severe cognitive impairment/dementia or severe global disability limiting the capacity of self-care, 5. Severe congestive cardiac failure (NYHA III-IV), 6. Severe renal disease, eGFR <30ml/min/1.73m^2), renal dialysis; awaiting renal transplant or transplant recipient, 7. Cancer diagnosis or treatment in past 2 years, 8. Need for oral anticoagulation at the time of randomization or planned in the future months, 9. Significant arrhythmias (including unresolved ventricular arrhythmias or atrial fibrillation) 10. Nursing/pregnant mothers, 11. Do not agree to the filing, forwarding and use of his/her pseudonymized data.

**D.4.5. Recruitment of study subjects:** A total number of 120 patients will be randomized (1:1) to treatment arms. Patients with stroke meeting inclusion/exclusion criteria will be recruited from the Family Medicine, Internal Medicine and Neurology outpatient clinics at KATH. Randomization will take place within 8 weeks of the index event (ischemic stroke) in a 1:1 ratio to one of the two arms: Polypill versus Usual care.

**D.4.6. Randomization Procedure:** Randomization of subjects in blocks of four will be conducted by a statistician ([name] PI) using a computer-generated random sequence of numbers. Consented participants will be assigned to either study arm at the baseline visit using the computer generated randomization sequence. The randomization sequence uses a minimization algorithm to ensure balance of prognostic factors such as stroke severity, average of 3 recorded baseline systolic BP measurements, & whether or not they are on background BP lowering agents, lipid modifiers & antithrombotic agents. Each sequence generated will be kept concealed in an envelope which will be opened by the Research Coordinator in the presence of the consenting study participant at enrollment.

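### The primary CIMT comparison is an unadjusted t-test on annualised change; baseline CIMT should be a fixed, pre-named covariate, for a modest gain in precision

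*Combined protocol and SAP*

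**What the plan says.** - **Outcome (D.4.9; Table 1 defines it the same way).** "The end of study CIMT value will be subtracted from the baseline CIMT value and divided by the length of follow-up".
- **Test (D.4.9).** "The rate of change in CIMT (mm/yr) between treatment arms will be tested with a two sided t-test". No covariate is named.
- **Baseline data.** D.4.7.5 schedules a carotid scan for every participant at baseline and at month 12. Lipids are taken at enrollment (D.4.7.2), and baseline systolic pressure is recorded before allocation (D.4.6).
- **Allocation (D.4.6).** The minimization algorithm aims at "balance of prognostic factors such as stroke severity, average of 3 recorded baseline systolic BP measurements" and background use of three drug classes. Baseline CIMT and baseline LDL-C are not named.
- **Regression (D.4.10).** Linear regression is mentioned for CIMT, as a way of estimating how covariates relate to outcomes. Candidates are screened one at a time at alpha 0.20, then kept or dropped by confounding, model-fit and standard-error rules. Baseline CIMT is not named, and nothing says whether the t-test or a regression is primary.
- **Risk-factor control (Table 1).** "Mean change in SBP at month 12 from baseline will be compared in the two treatment groups". LDL-C is worded the same way. No model is given for either.

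**The concern.** Change from baseline removes the baseline value with a fixed coefficient of one. When the two scans are imperfectly correlated, that coefficient is too large: patients with high first readings tend to show smaller increases, so the change score is negatively correlated with its own baseline. There are two consequences. The arm comparison carries more variance than it needs to. And if the arms happen to differ at baseline, the raw-change estimate moves in a predictable direction.

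A linear model with baseline CIMT as a covariate estimates the coefficient from the data and removes both effects. The baseline scan is already paid for, so the question is only whether the plan commits to using it this way. As written it does not: adjustment would depend on choices made after outcomes are seen.

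**Working it through.** **Inputs from the documents**
- SD of the annual rate 0.035 mm/yr and rate in treated patients 0.085 mm/yr: "The rate of change in common CIMT in treated patients is around 0.085 mm/yr with a standard deviation of 0.035".
- Polypill arm: "an assumed rate of change of 0.0825 mm/yr".
- Two-sided alpha 0.05, power 90%, 82 patients, 20% drop-out (D.4.9).
- Enrolment: "A total number of 120 patients will be randomized (1:1) to treatment arms". With 20% loss, 120 × 0.8 = 96 analysed, or 48 per arm.

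**Assumptions.** Rho between the two scans is not given, so a range is shown. CIMT variance is taken as equal at both scans, the interval as one year, and the SD of change is held at 0.035.

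**Step 1: the plan's own figure.** n per arm = 2(1.960 + 1.282)² × SD² / difference².
- Printed difference, 0.085 − 0.0825 = 0.0025: n = 4,119 per arm, 8,238 in total. This does not give 82.
- Difference 0.025: n = 41.19, rounded up to 42 per arm, 84 in total, which is close to 82. That 0.025 was intended is an inference, used here only to put power on a scale consistent with 82 patients.

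**Step 2: precision.** With s the SD of CIMT at either scan:
- Var(change) = 2(1 − rho)s²
- Var(baseline-adjusted) = (1 − rho²)s²
- Ratio = (1 + rho)/2

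Power below is from the noncentral t at 41 per arm. The unadjusted standardized difference is 0.025/0.035 = 0.714, giving 89.2%. The adjusted one is 0.714/√((1 + rho)/2).

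| rho | Variance ratio | Reduction | Power, adjusted | Implied baseline SD, 0.035/√(2(1 − rho)) |
|---|---|---|---|---|
| 0.5 | 0.75 | 25% | 95.8% | 0.035 mm |
| 0.7 | 0.85 | 15% | 93.4% | 0.045 mm |
| 0.9 | 0.95 | 5% | 90.6% | 0.078 mm |
| 0.95 | 0.975 | 2.5% | about 90% | 0.111 mm |

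**Step 3: which rho is credible.** The last column shows the between-patient spread each rho requires. A baseline SD of 0.035 to 0.045 mm is about half of one year's assumed progression (0.085 mm), in adults of any age above 18 with several ischemic subtypes, scanned at 0.10 mm axial resolution. A wider spread is easier to believe. If the baseline SD is 0.10 to 0.15 mm (an assumption), rho = 1 − 0.035²/(2 × SD²) is 0.94 to 0.97. The variance reduction is then about 3% to 1.4%, and power is about 90% against 89%.

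**Step 4: chance imbalance.** A one-standard-error baseline difference shifts the raw-change estimate by (1 − rho) × s × √(2/48), in absolute size:
- rho 0.5: 0.0036 mm
- rho 0.7: 0.0028 mm
- rho 0.9: 0.0016 mm

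Against 0.025 mm/yr this is 14%, 11% and 6%. The t-test's own standard error is 0.035 × √(2/48) = 0.0071, so the shift is 0.50, 0.39 and 0.22 of a standard error.

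With a larger imbalance of 1.96 standard errors (41 per arm), the conditional type I error is 12.9%, 9.8% and 6.6% at rho 0.5, 0.7 and 0.9. Averaged over all randomizations it remains 5%.

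**Step 5: does adjustment rescue the printed difference?** No. At 0.0025 mm/yr the adjusted analysis still needs 3,090 per arm (rho 0.5) to 4,016 per arm (rho 0.95), and power at 41 per arm stays around 5–6%.

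**The case against.** The strongest reply is that nothing is invalid. Randomization makes the raw-change t-test unbiased, its confidence interval already allows for chance imbalance, and if rho is about 0.9 or higher the gain is a few percent. All of that stands, and it limits the point to a modest improvement in precision.

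D.4.10 is a second reply, since it plans regression for CIMT. The correlation of change with baseline is −√((1 − rho)/2). If baseline CIMT were a candidate, it would therefore pass the 0.20 screen with over 99% probability at rho 0.5 to 0.7, and about 80% at rho 0.9 (82 to 96 patients). But it is not named as a candidate, later rules could drop it, and the regression is not said to be the primary comparison. Likely entry by selection is not pre-specification.

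Several stronger readings are tempting and are not supported:
- *Baseline values go unused.* They are subtracted; what is missing is the covariate term.
- *Chance imbalance can move the estimate by as much as the planned difference.* That holds only at the lower correlations and against the printed 0.0025, which is inconsistent with 82 patients.
- *The imbalance argument applies equally to SBP.* Baseline SBP is a minimization factor, so only the precision argument carries over.
- *The quality-of-life, cognition and depression scales share the fault.* Table 1 states no raw-change comparison for EQ-5D, MoCA or the depression scales.
- *Annualising lets noisy early scans into the analysis.* D.4.7.5 schedules scans only at baseline and month 12; no earlier scan is planned.

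**Conclusion.** The point holds in a limited form. The only test named for the primary outcome is unadjusted, and no section fixes baseline CIMT as a covariate. The cost is lost precision and conditional sensitivity to baseline imbalance, not bias or an inflated overall type I error.

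The size rests on an unstated rho and on equal variances at the two scans. The 25% reduction is the optimistic end of the range; a few percent is more likely given a change SD of 0.035. The power figures also rest on reading the difference as 0.025 mm/yr, which the sponsor would have to confirm.

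A reader might infer that adjustment would make the sample size adequate for the printed difference. It would not: that mismatch is a separate and larger problem. The change is still worth making, because it costs nothing and removes a decision that would otherwise be taken with outcome data in hand.

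**What to change.** 1. In D.4.9 and D.4.10, name one primary analysis: a linear model for month-12 CIMT (or annualised change) on treatment arm, with baseline CIMT as a fixed, pre-named covariate and the minimization factors from D.4.6. Report the adjusted arm difference with its 95% CI. Because D.4.6 introduces its factors only as examples, close that list first.
2. Keep the unadjusted t-test on the mm/yr rate as a sensitivity analysis.
3. State that the alpha 0.20 screen and later selection rules are not used for this comparison.
4. In Table 1, compare SBP and LDL-C by a model of the month-12 value on arm plus baseline value. For SBP the reason is precision.

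The cost is a revision of the analysis wording, with Table 1 aligned to it. No new measurements or patients are needed.

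### Section D.4.9: the printed CIMT rates and SD do not give 82 patients for 90% power; taken as printed they need about 8,240 and give about 6% power

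*Combined protocol and SAP*

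**What the plan says.** Section D.4.9 of the combined protocol and SAP contains the whole justification for the primary endpoint. The outcome is the annualised change in CIMT: "The end of study CIMT value will be subtracted from the baseline CIMT value and divided by the length of follow-up". The test is also named: "The rate of change in CIMT (mm/yr) between treatment arms will be tested with a two sided t-test".

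The inputs follow. For the reference rate: "The rate of change in common CIMT in treated patients is around 0.085 mm/yr with a standard deviation of 0.035". For the polypill arm: "We assume that polypill improvement leads to a halting of CIMT progression with an assumed rate of change of 0.0825 mm/yr". The conclusion is "With a two sided alpha of 0.05 and a 90% power we need 82 patients (104 patients with 20% drop-out rate").

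Section D.4.5 sets enrolment somewhat higher: "A total number of 120 patients will be randomized (1:1) to treatment arms".

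The aim is worded more strongly than a small slowing. Aim 1 in D.4 asks whether the polypill strategy "will result in carotid intimal media thickness stabilization/regression among recent stroke patients at one year after an index ischemic stroke", and the overview in D.1 asks whether the polypill "would result in carotid intimal thickness regression, improved adherence, and tolerability". No other section gives a CIMT effect size.

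**The concern.** The inputs and the answer stand in one paragraph and do not fit together. A difference of 0.085 − 0.0825 = 0.0025 mm/yr against an SD of 0.035 is very small, and 41 patients per arm cannot detect it with 90% power.

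The words conflict with the number as well. If positive values mean thickening, going from 0.085 to 0.0825 slows progression by 0.0025/0.085 = 2.9%. That is neither a halt nor the stabilization or regression named in the aims.

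This paragraph is the only support for the 90% power claim on the primary endpoint. Without knowing the effect it was built on, a reader cannot judge what a null CIMT result rules out. The trial is also meant to inform a phase 3 design.

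**Working it through.** **Inputs (all from D.4.9 unless noted).** Rates 0.085 and 0.0825 mm/yr; SD 0.035, assumed equal in both arms because only one is printed; two-sided alpha 0.05; power 90%; 1:1 allocation and 120 randomized (D.4.5); drop-out 20%.

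**Formula.** Normal approximation: n per arm = 2 × [(1.960 + 1.282) × SD / difference]². Exact values and powers come from the noncentral t distribution, since D.4.9 names a t-test.

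**1. What reproduces the plan's 82.** With SD/difference = 1.4 (standardized effect 0.714), n = 2 × (3.242 × 1.4)² = 41.2 per arm, or 82.4 in total. Two sets of inputs give that ratio:
- difference 0.025 with SD 0.035;
- difference 0.0025 with SD 0.0035.

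The exact t-test needs 43 per arm (86 in total); at 41 per arm its power is 89.2%. The drop-out step also reproduces: 41/0.8 = 51.25, rounded up to 52 per arm, gives 104.

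**2. The inputs as printed.** SD/difference = 0.035/0.0025 = 14 (standardized effect 0.071). Then n = 2 × (3.242 × 14)² = 4,118.9 per arm by the normal approximation. The exact t-test needs 4,120 per arm, or 8,240 in total. That is about 100 times the stated 82 (8,240/82 = 100.5).

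**3. Power by two-sided t-test.**

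| Evaluable patients | Effect 0.071 (as printed) | Effect 0.714 |
|---|---|---|
| 82 | 6.2% | 89.2% |
| 96 (120 × 0.8) | 6.4% | 93.4% |
| 120 | 6.7% | 97.3% |

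**4. Other readings of the printed figures.**

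| Reading | Result |
|---|---|
| One-sided alpha 0.05, 90% power | 6,716 in total |
| Two-sided, 80% power | about 6,156 in total |
| One-sided, 80% power | about 4,850 in total |
| One-sample formula | 2,060 |
| 82 taken as per arm | power 7.4% |
| Full halt (difference 0.085) | about 5 per arm |
| 0.0825 taken as the reduction, leaving 0.0025 mm/yr | about 5 per arm |

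None gives 82 in total or 90% power. Reading 0.0825 as the reduction would suit the word *halting*, but it misses 82 in the other direction.

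**5. Detectable difference with 96 evaluable (48 per arm).** It is 0.669 SD at 90% power and 0.578 SD at 80%:
- if the SD is 0.035: 0.0234 and 0.0202 mm/yr;
- if the SD is 0.0035: 0.00234 and 0.00202 mm/yr.

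The two candidate corrections therefore imply detectable effects that differ tenfold.

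**The case against.** The best defence is that this is a misprint in an adequately sized trial. The stated 82 follows almost exactly from an effect of 0.714, 104 follows from 82, and 120 exceeds 104. On that view, leading with 8,240 patients and 6% power overstates the problem. Much of this is fair: the pattern does point to a wrong input more than to an underpowered design. But the documents do not say which input is wrong, and the choice changes the target effect or the SD tenfold. Even accepting a difference of 0.025 does not fix the polypill rate, since 0.085 against 0.060 and 0.025 against 0 both give it (the latter would require 0.085 to be wrong too).

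Three smaller objections are correct but change no conclusion:
- **Sign.** D.4.9 subtracts the final value from baseline, so taken literally a positive rate is thinning. Describing 0.0825 as a slowing assumes that positive means progression. If the two rates had opposite signs, the difference would be 0.085 + 0.0825 = 0.1675 mm/yr and about 3 per arm would suffice, which is again not 82.
- **Reference group.** The rate of 0.085 is given for treated patients, and equating them with usual care is an inference. It does not alter the calculation.
- **Covariate adjustment.** D.4.10 mentions regression models, but cutting 8,240 to 82 would require covariates that explain about 99% of the outcome variance (1 − 82/8,240), and D.4.9 sizes an unadjusted t-test.

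Pilot status and the feasibility case for 120 are also relevant. They could justify enrolling 120 without a power claim, but they do not support the 90% claim that the plan makes.

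**Conclusion.** The concern holds, with high confidence, and must be fixed. The 90% power statement for the primary endpoint is contradicted about 100-fold by its own inputs: 8,240 patients against 82, or 6.2% power against 90%. This rests on a common SD of 0.035 in both arms and on reading the two printed rates as the arm means. No alternative reading tried recovers the stated figure.

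It does not follow that the trial is underpowered. The 6% applies only if the printed figures are really meant. If the intended standardized effect was about 0.71, the planned enrolment is sufficient and the error lies in the stated inputs. The documents cannot settle which.

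**What to change.** Revise D.4.9 as follows.

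1. State the intended usual-care rate, polypill rate and SD, each with its source. The reference rate and SD already carry a citation, which should be rechecked; 0.0825 has none. State whether positive values mean thickening or thinning.
2. Recompute sample size and power from those figures, using the t-test that the section names.
3. Base the statement on the 120 to be randomized (96 evaluable after 20% drop-out), and give the detectable difference for the confirmed SD: about 0.023 mm/yr at 90% power and 0.020 at 80% if the SD is 0.035, or 0.0023 and 0.0020 if it is 0.0035.
4. Make the description of the effect agree with the numbers and with Aim 1.
5. If 0.0825 and SD 0.035 are really meant, withdraw the 90% claim and state power of about 6%.

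The work is a check of source figures and a text correction, with no added patients. What it costs the plan depends on which figure was wrong: a stated effect ten times larger (0.025 mm/yr), a very small SD (0.0035) that has to be justified from its source, or an admitted power of about 6%.
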